Strategies to prevent these interactions to reduce the incidence of *S. pneumoniae* and RSV infection are very important in children as well as the elderly. The elderly might colonize with *S. pneumoniae* first and then get the RSV acquisition from the younger households. Vaccine delivery should be justified by detailed understanding of *S. pneumoniae* and RSV transmission dynamics. The determinants include carriage rate, age distribution, infection severity, and presence of concurrent *S. pneumoniae* or RSV in the same household. This household-based prospective cohort study aims to establish the household transmission of RSV and *S. pneumoniae* especially in the elderly and infants/children as well as inter-relationship between *S. pneumoniae* and RSV. We hope our data can be utilized in the AI fields to develop a model to predict the transmissions in the exceedingly early stage of disease of *S. pneumoniae* and RSV and strategy of prevention.

Preliminary Data

Our previous data suggest that interactions between RSV and *S. pneumoniae*. RSV infections can increase the ability of adherence of *S. pneumoniae* 15 A in Hep2 cell.

We selected 13 patients for the RSV genotype and 16S ribosomal RNA test. The 16SrRNA revealed *S. pneumoniae* was the predominant bacterial in the nasopharyngeal site.

[figure not shown]
RSV	RSV genotype	16SrRNA
A	ON1	Streptococcus pneumoniae
B	BA9	Streptococcus pneumoniae
A	ON1	Streptococcus pneumoniae
B	BA9	Haemophilus influenzae
A	ON1	Streptococcus salivarius
B	BA9	Streptococcus thermophilus
A	ON1	Streptococcus pneumoniae
B	BA9	Streptococcus lactarius
B	BA9	Streptococcus pneumoniae
A	ON1	Streptococcus pneumoniae
B	BA9	Streptococcus pneumoniae
B	BA9	Propionibacterium acnes
B	BA9	Streptococcus pneumoniae

Study site and population

A **household-based prospective cohort** study will be conducted from 2021 to 2025 in northern Taiwan. We will invite 240 households, having a baby who is discharged from MacKay children's Hospital.

Around 20 babies per months for 12 months adding up to 240 babies in total. The estimation is based on historical discharge number from NBR MacKay Memorial Hospital Taipei. The number is also proved feasible in previous studies.

[figure not shown]
* nuclear family: a couple and their dependent children, regarded as a basic social unit.

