+ extended family: a family that extends beyond the nuclear family, including grandparents, aunts, uncles, and other relatives, who all live nearby or in one household.

Patient recruitment and management

The households will be classified into nuclear family type and extended family type. The "Nuclear family type" is defined as husband and wife with baby (aged less than 5 months) and with or without children (2-5) and the "Extended family type" (three-generation family) is defined as husband and wife with baby (aged less than 5 months), children (2-5), and grandparents aged > 65 years old. The exclusion criteria are co-morbid medical conditions of the baby such as chronic lung disease, cyanotic congenital heart disease, neuromuscular disease and a primary immunodeficiency. We will initially complete an enrollment form to collect baseline data, including patient demographics, prior medical history, season when discharge, neonatal course and households. A LINE-based management will be done weekly by study team to see if there are any respiratory symptoms in household. In addition to the monthly physician weekly LINE response, the research nurse will contact the parents or legal guardians by telephone monthly for the 24 months to obtain data on changes in baseline information, and specific facts regarding possible respiratory infections after the last contact.

Study endpoint

The primary endpoint is the *S. pneumoniae* and RSV isolation rates in children and their household contacts of different family type. The secondary endpoint is the serotype of *S. pneumoniae* and RSV in post-PCV13 era.

Study design

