Households with at least 1 ARI case during the study period will be included for data analysis. A household with ARI in different years will be treated as 2 different households. Because household visits will be conducted weekly, we will collect specimens for ARI episodes as possible. We will identify these ARI through symptom records. The ARI cases in RSV or *S. pneumoniae* whose dates of onset are within 10 days before or after RSV or *S. pneumoniae* onset will be identified and defined as preceding and subsequent ARI, respectively. We will apply a Bayesian approach to estimate acquisition and clearance rates for RSV or *S. pneumoniae* in a susceptible-infected-susceptible model [37]. The inference relies on repeated measurements of the current status of being a non-carrier (susceptible) or a carrier (infected) of one of the pathogens. We will collect the measurements with sampling intervals. The index cases are the first members of the household to have clinically apparent illness confirmed by laboratory studies. The secondary cases are defined as other family members whose respiratory symptoms occurred later than the index cases' illness. Identified source of infection within the household is defined as the first case in the household who displayed clinically apparent disease and who have clear contact history with individuals outside the household who had illnesses suggestive of *S. pneumoniae* or RSV infection. The infection transmission interval will be defined as the time between the onset of disease for the first case in the household and the onset of disease in a secondary case [38].

Hierarchical generalized linear mixed effect models (HGLMEM)

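### Index case, secondary case and transmission interval are defined per household with only a yearly restart, so later separate introductions in a year have no index and onset pairs across a year boundary are cut

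*Combined protocol and SAP*

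**What the plan says.** All the relevant rules are in the combined protocol and SAP, Statistical Methods, Infected model.

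- Inclusion: "Households with at least 1 ARI case during the study period will be included for data analysis".
- Restart: "A household with ARI in different years will be treated as 2 different households". The section does not say whether a year is a calendar year, a year of follow-up or a season.
- Index: "The index cases are the first members of the household to have clinically apparent illness confirmed by laboratory studies".
- Secondary: "The secondary cases are defined as other family members whose respiratory symptoms occurred later than the index cases' illness".
- Transmission interval: "the time between the onset of disease for the first case in the household and the onset of disease in a secondary case".
- The only time window in the section takes respiratory illnesses "whose dates of onset are within 10 days before or after RSV or" pneumococcal onset and labels them preceding or subsequent. It does not assign index or secondary status.

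On duration, Patient recruitment and management has the research nurse "contact the parents or legal guardians by telephone monthly for the 24 months". Study site and population describes staggered entry: "Around 20 babies per months for 12 months adding up to 240 babies in total".

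**The concern.** A household followed for two years can have several unrelated introductions of RSV or pneumococcus. The Background itself notes that repeat RSV infection of one person within a season has been documented. A transmission analysis needs to know who brought in each one and who caught it from whom. The definitions are tied to the household, and none mentions an episode, a pathogen or a maximum interval. Only a change of year produces a new first case.

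Two errors follow. Separate introductions in one year are merged under the first index, and a chain that crosses a year boundary is split between two nominal households. At stake are the identified source of infection and the transmission interval. Both bear on the aim stated under Significance: to establish household transmission, especially involving the elderly and young children.

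**Working it through.** The plan gives no figure for introductions or intervals, and the sample-size section does not use them, so there is nothing of the plan's own to reproduce. The check applies the definitions literally and then sizes the effect under stated assumptions.

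**1. Two introductions in one year (invented dates, calendar year).** A sibling is RSV-positive on 10 February. The grandmother is separately RSV-positive on 20 October, and the baby falls ill on 25 October.
- The index is the sibling, the first confirmed member.
- The grandmother is another member with later symptoms, so she is secondary, at 252 days.
- The baby is secondary at 257 days, although the October onsets are 5 days apart.
- Had the sibling also brought in the October infection, that illness would fit neither label, because secondary cases are restricted to other members.

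Within one household-year the recorded interval can reach about 364 days. Requiring confirmation, a type match or a maximum interval for secondary cases would remove false secondaries, but the October introduction would still have no index.

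**2. A chain across a boundary (invented dates).** The mother is RSV-positive on 29 December and the baby falls ill on 3 January. Under calendar years these are two households and the pair is lost. The baby becomes an index only if laboratory-confirmed and first in the new unit.

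**3. Share of introductions without an index.** Assume introductions per unit are Poisson with mean m. Each unit with at least one introduction supplies one first introduction, so the share that is not first is 1 − (1 − e^(−m))/m. With the year split, m is the yearly rate; with one 24-month unit, it is twice that.

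| Introductions per household-year (assumed) | Year split | One 24-month unit |
|---|---|---|
| 0.5 | 1 − 0.393/0.5 = 21% | 1 − 0.632/1 = 37% |
| 1 | 1 − 0.632/1 = 37% | 1 − 0.865/2 = 57% |
| 2 | 1 − 0.865/2 = 57% | 1 − 0.982/4 = 75% |

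The merging therefore comes from the per-household definitions, and the year rule reduces it. If the definitions are meant to be read separately by pathogen, m is the rate for one pathogen. Variation in rates between households would raise these shares at the same mean.

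**4. Pairs cut at the boundary.** With onsets spread evenly and one boundary every 365 days, a pair s days apart is cut with probability s/365:
- 5 days: 5/365 = 1.4%
- 10 days: 10/365 = 2.7%
- 14 days: 14/365 = 3.8%

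Clustering of cases around the boundary would raise these figures. If years are follow-up years, a 24-month period has one interior boundary in 730 days, which halves them (5/730 = 0.7%; 14/730 = 1.9%).

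**5. Number of units.** If years are calendar years, any 24-month follow-up not starting on 1 January touches three of them, whereas the rule provides for two households. If they are follow-up years, two is right.

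**The case against.** The strongest reply is that the plan does work by episode in practice. The Study design table ties index status to a presentation with symptoms, has a stage after the first episode, and repeats clinical and laboratory assessment when new symptoms appear. The follow-up calls at 2, 4 and 8 weeks fit that reading, and the index definition is in the plural. This shows that several episodes are expected. It does not say when a new episode starts or who is then the index, and the plural allows tied first cases rather than a later one. The calls are a data-collection schedule.

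Three stronger readings are tempting, and the documents do not support them.

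- **That the year split creates the merging.** It lessens it, as the table above shows. The split itself causes only the small boundary cut.
- **That the family-type comparison is biased.** With assumed means of 1 in nuclear and 2 in extended families, 63% and 43% of introductions would keep an index, but the documents give neither rate. The only family-type figures, in Power/Sample Size, are 29-46% and 38-50% for household-acquired infection, which is not introduction. Used purely for scale, with m = −ln(1 − p), the share kept is 85% against 79% at the lower ends, 75% against 72% at the upper ends, and 85% against 72% for the widest pairing. A difference is possible but not shown.
- **That the main results fail.** The primary endpoint is isolation rates. The susceptible-infected-susceptible model and the mixed model are both described in terms of individual infection status over time, and neither is said to use index labels.

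**Conclusion.** The point stands as a defect in the case definitions. Followed as written, they give wrong source and interval results whenever a household has more than one introduction in a year, and nothing elsewhere in the document repairs this. The year rule softens that problem and adds a small one of its own, about 1% to 4% of onset pairs at intervals of 5 to 14 days under uniform timing and a yearly boundary.

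The size of the main effect cannot be fixed from the documents. The 21% to 57% range rests on assumed rates of 0.5 to 2 introductions per household-year and a Poisson count. The harm is confined to source of infection and transmission interval. It is worth correcting before analysis, but it is no ground for doubting the primary endpoint.

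**What to change.** Replace the year rule in the Infected model section with an episode rule:

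- Define household episodes separately for RSV and *S. pneumoniae*. An episode starts at a laboratory-confirmed onset that follows a stated gap with no onset linked to that pathogen in the household. State what counts as linked.
- Assign the index case, secondary cases and transmission interval within the episode.
- Number episodes within the enrolled household, and keep that household as one cluster across years.

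The gap should be pathogen-specific. A gap free of any respiratory symptom would merge unrelated illnesses in families with frequent colds. The existing 10-day window was written for another purpose and should not be carried over without justification.

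The cost is a change of plan wording and one derived variable built from the symptom records and laboratory results already planned. Visits and sample size do not change. The drawback is that the gap length is a judgement, so fix it before the data are examined and report one alternative gap as a sensitivity analysis.

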Respiratory syncytial virus (RSV) infection causes lower respiratory tract infection such as bronchiolitis and pneumonia and is the leading cause of hospitalization of infants and young children [6-8]. After testing for viruses, bacteria, and fungi in children with severe hospitalized pneumonia, the study found that 61% of severe pneumonia cases are caused by viruses led by RSV, which alone accounted for 31% of cases[9]. In recent years, improvement in the sensitivity and specificity of molecular methods has provided new opportunities to delineate the causative CAP pathogens [10, 11]. In addition to *S. pneumoniae*, non-typeable *Haemophilus influenzae*, and *Moraxella catarrhalis* are the common etiologies [12, 13], RSV is associated with the common bacterial pathogens causing AOM [14]. The nasopharyngeal microbiota composition characterized by *H. influenzae* and *S. pneumoniae*, is associated with a distinct host inflammatory immune response and enhanced disease severity as defined by more frequent need for RSV hospitalization. Altogether, the data suggest that viral-bacterial interactions within the ecological respiratory niche modulate the systemic host immune response to RSV, thereby potentially influencing disease phenotypes [15]. This has also helped to uncover the interplay among the different pathogens during acute respiratory infections [11, 16].

In the post-pneumococcal conjugate vaccine era, seasonal increases in RSV, influenza virus, and human metapneumovirus infections in children were associated with increased pediatric admissions with invasive pneumococcal disease, especially pneumonia caused by nonvaccine serotypes [17]. Co-detection of RSV and *S. pneumoniae* in the nasopharynx was associated with more severe ARI, suggesting that *S. pneumoniae* colonization plays a pathogenic role in young children[18]. Also, pneumococcal colonization can enhance subsequent RSV infection [19]. Besides, invasive serotype colonization was significantly lower in RSV positive CAP, whereas colonization with noninvasive serotypes such as serotype 33 F tended to be higher in RSV positive CAP [20]. The serotype of *S. pneumoniae* is changing in the post-pneumococcal conjugate vaccine era in Taiwan, the effect of RSV infection for the efficacy of pneumococcal conjugate vaccine needs further study.

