Asymptomatic carriage of *S. pneumoniae* in the nasopharynx is a prerequisite for disease. In the previous study, adults acquire *S. pneumoniae* relatively more in the household than other age groups, and transmissions within household were mostly seen from older to younger siblings [21]. Oropharyngeal colonization is 65.8% of *S. pneumoniae* autolysin (lytA) gene sequence [22]. RSV has become an increasingly documented cause of illness in adults and optimal diagnosis requires reverse transcription polymerase chain reaction (RT-PCR) assays or serology [23].

Close contacts within households may present potential opportunities for RSV transmission [24]. Studies have shown that family members of infants, such as older siblings and parents, are an important RSV infection source in the infants [25, 26]. In about 50% of households, more than one person is infected, and repeat infections in the same individual from homologous or heterologous RSV subtypes within the same season are documented [27]. The identification of RSV infections and increased awareness of the prominent role this respiratory virus has in relatively severe illness in adults by using molecular testing [28, 29]. Besides, the direct interaction between RSV protein and the pneumococcus might result in increased bacterial virulence and worsening disease outcome in respiratory infection [30]. On the other hand, *S. pneumoniae* colonization can enhance subsequent RSV infection [19]. The interactions occurring between *S. pneumoniae* and RSV during respiratory infections and pneumococcal acquisition indicate that pneumococcal serotypes have different ability to cause infection as well as coinfections [31].

[figure not shown]

Significance

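### The SIS transmission model needs repeated infection status, but every specimen with a stated time is triggered by illness, and the plan does not say how the fit handles that trigger

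*Combined protocol and SAP*

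**What the plan says.** Statistical Methods, Infected model, plans a Bayesian SIS model for acquisition and clearance. It states that "The inference relies on repeated measurements of the current status of being a non-carrier (susceptible) or a carrier (infected) of one of the pathogens", and adds: "We will collect the measurements with sampling intervals". No interval, visit list or set of persons to be sampled is given. The same section says: "Because household visits will be conducted weekly, we will collect specimens for ARI episodes as possible". It keeps only households with at least one acute respiratory infection (ARI).

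The operational sections describe something different. Under Patient recruitment and management the weekly contact is remote: "A LINE-based management will be done weekly by study team to see if there are any respiratory symptoms in household". The Study design text and table tie specimens to respiratory illness, and the section on multiplex PCR places swabs within 48 hours of symptoms.

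On case definitions, the Infected model section says "The secondary cases are defined as other family members whose respiratory symptoms occurred later than the index" case's illness. For preceding and subsequent ARI, but not for secondary cases, it sets a window: cases "whose dates of onset are within 10 days before or after RSV or *S. pneumoniae* onset".

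The section on hierarchical mixed models (HGLMEM) adjusts for a baseline assessment of infection status.

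**The concern.** An SIS fit reads the rates from status at successive swabs. If the swab times carry no information about status, the illness trigger costs only precision. If a person is more likely to be swabbed because of being infected at that moment, positives are over-represented and an ordinary fit attributes the excess to the transmission rates.

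The Background gives reason to expect this for RSV: "Respiratory syncytial virus (RSV) infection causes lower respiratory tract infection such as bronchiolitis and pneumonia". For pneumococcus it is less clear, because the same section says that "Asymptomatic carriage of *S. pneumoniae* in the nasopharynx is a prerequisite for disease": carriage without symptoms triggers no swab of the carrier.

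The rates at stake are not listed under Study endpoint. They are, however, the planned output of the transmission model, and the Significance section makes household transmission the aim of the study.

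**Working it through.** The documents give no acquisition rate, clearance rate or swab count, so there is no planned figure to reproduce. All rates below are assumptions. The simulations show whether bias arises and in which direction, not its size in this study.

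**1. Sampling occasions set side by side**

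| Occasion | Specimen | Trigger |
|---|---|---|
| Enrollment (table) | none listed | – |
| Weekly LINE contact (table; LINE management) | none listed | – |
| Person has respiratory symptoms (Study design) | swab; urine in adults | own illness |
| Index case has pneumonia or lower-tract illness (Study design, table) | further specimens from index; swab and urine from family | index illness |
| Weeks 2, 4 and 8 (Study design, table) | none; interview | – |
| New symptoms in that follow-up | laboratory work repeated | member's illness |

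Family screening reaches contacts without symptoms, but an index illness sets its timing.

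**2. Mechanism.** Let acquisition be λ, clearance μ, and the swab rate while infected r times the rate while uninfected. True prevalence is λ/(λ+μ); the positive fraction among swabs is rλ/(rλ+μ). With assumed λ = 0.25 and μ = 0.50 per month, prevalence is 0.25/0.75 = 0.333. At r = 2 the positive fraction is 0.50/(0.50+0.50) = 0.500.

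**3. Two-state check.** 10,000 independent persons, 24 months, 0.4 illness swabs per month while uninfected, same λ and μ, likelihood ignoring the trigger. Estimated/true acquisition and clearance:
- r = 0.5: 0.73 and 1.29
- r = 1: 1.00 and 1.01
- r = 1.5: 1.17 and 0.88
- r = 2: 1.27 and 0.80
- r = 3: 1.41 and 0.71

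Fixed monthly swabs gave 0.249 and 0.500 per month, close to the true values.

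**4. Pneumococcus, household simulation.** 240 households (120 of 3–4 and 120 of 5–6 members, assumed from the family-type definitions), 730 days, carriage 30 or 60 days, prevalence 20% or 40%, 2 or 4 symptom swabs a year while not carrying, 0% or 50% of acquisition from within the household. In the contact-swab runs, 20% of swabbed episodes trigger swabs of all members. Ranges are over 16 settings, each the median of 5 runs.

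| Symptom ratio | Acquisition, no contact swabs | Clearance, no contact swabs | Acquisition, contact swabs | Clearance, contact swabs |
|---|---|---|---|---|
| 0.7 | 0.72–0.89 | 1.03–1.29 | 0.85–0.97 | 1.00–1.14 |
| 1 | 0.91–1.12 | 0.93–1.15 | 0.91–1.05 | 0.90–1.02 |
| 1.5 | 1.10–1.34 | 0.78–0.94 | 1.05–1.20 | 0.88–0.95 |
| 2 | 1.21–1.48 | 0.70–0.81 | 1.14–1.29 | 0.83–0.92 |

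The spread at ratio 1 shows that range ends of about 10% or less are within simulation noise.

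**5. RSV.** 10-day infection, 0.5 acquisitions a year, 30% or 60% swabbed 2–4 days after onset, 1, 2 or 4 other symptom swabs a year, contact swabs 0% or 20%, household share 0% or 50%; 24 settings of 10 runs. Acquisition medians were 2.15–24.23 times the truth. With no infection-triggered swabs they were 0.94–0.98. Repeat simulations on similar assumptions gave 2.9–27.1, 3.2–20 and 3–18. Clearance medians were 0.81–1.54, so no direction is claimed. With a constant swab rate through infection (λ = 0.05, μ = 3.0 per month), acquisition was only 1.16–2.20 at r = 1.5–5.

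**6. Does modelling the trigger work?** A likelihood with one swab rate per state gave, for pneumococcus over all ratios, acquisition 0.88–1.23 and clearance 0.87–1.16 without contact swabs, and 0.92–1.08 and 0.87–1.06 with them. For RSV swabbed near onset the same approach left acquisition 2.2–20.7 times the truth (2.5–14 and 2.7–17 in repeat simulations). When the RSV swab rate really was constant during infection, it recovered acquisition (0.96–1.02). The failure comes from swabs clustering at onset.

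**7. Secondary-case definition.** Chance that a contact has a later unrelated ARI = 1 − exp(−rate × time), at an assumed 1–4 unrelated ARIs per person-year:
- 10 days (10/365 year): 1 − exp(−0.027) = 2.7% to 1 − exp(−0.110) = 10.4%
- 8 weeks (56/365 year): 1 − exp(−0.153) = 14% to 1 − exp(−0.614) = 46%
- 6–12 months left, no window: 1 − exp(−0.5) = 39% to 1 − exp(−4) = 98%

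**The case against.** **The plan may not intend a naive fit.** This stands. Silence is under-specification, the cited SIS method cannot be seen from the documents, and figures are not shown, so a schedule there cannot be excluded. A reader might infer that routine swabs will not be taken, or that the trigger will be ignored; the documents support neither. They support only that no symptom-independent specimen and no handling of the trigger is described.

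**Illness-triggered sampling need not bias.** This also stands. Sampling that depends only on results already observed can be ignorable; the problem is dependence on current, unobserved status. Swabs for ARI of other causes, and of contacts without symptoms, also supply negatives. It would be tempting to say that both pathogens' rates must come out too high. For pneumococcus that holds only if carriage raises the chance of a sampled illness. With contact swabs, the acquisition medians exceed the truth by at most 20% at ratios 1 to 1.5.

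**The RSV factor is a product of the inputs.** Accepted. A reader might take about twofold as a minimum; the 1.16 in step 5 shows that it is not.

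**Secondary cases are followed for 8 weeks, and symptomatic members are tested.** Study design does say this, so 39–98% should not be read as the expected misclassification. The case definition itself uses neither the test result nor the 8-week limit.

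**Conclusion.** The concern holds in conditional form. The SIS model is specified on repeated status, the documented specimens are all illness-triggered, and the weekly household visits in the Infected model section do not match the weekly LINE contact described elsewhere. If the swab times are treated as uninformative:
- RSV acquisition is overestimated when swabs follow onset, by a factor that rests on assumed inputs.
- Pneumococcal acquisition is overestimated and clearance underestimated when the symptom ratio exceeds 1. There is little bias at 1, and the direction reverses below 1.

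The ratio is not in the documents, so the size in this study is unknown. A reader might infer that the primary result is undermined. The documents do not support that, since these rates are not a primary or secondary endpoint. The point should be fixed before the transmission model is fitted.

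Separately, the secondary-case definition needs no test, pathogen match or window. At the assumed ARI rates it would admit 14–46% of contacts by chance if 8 weeks is the working window. As a minor matter, the baseline infection status in the mixed model is not tied to any listed specimen.

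**What to change.** 1. Reconcile the Infected model section with Patient recruitment and management, Study design and LINE management. If a symptom-independent specimen schedule exists, state it.
2. If none exists, treat the pathogens separately.
   - *Pneumococcus:* put a symptom-dependent swab rate into the likelihood, enter contact-screening swabs as status readings only, and report a sensitivity range for the symptom ratio that includes 1 and values below 1, with the limitation stated.
   - *RSV:* do not use a constant swab rate per state. Either model onset-linked swabbing explicitly, or limit the estimand to laboratory-confirmed symptomatic infection and household secondary transmission conditioned on the index case.
3. As a separate correction, amend the secondary-case definition to require laboratory confirmation of the same pathogen (and serotype or subgroup where available) within a stated, pathogen-specific window.
4. As a minor correction, define baseline infection status in the HGLMEM section from a specimen actually collected and not also used as an outcome, or delete the covariate.

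These are text and analysis edits and need no new swabs. The costs are:
- The pneumococcal rates will depend on the assumed symptom ratio and on swabbing completeness not differing by status.
- The restricted RSV estimand gives up RSV acquisition and clearance rates.
- Untested contacts cannot count as secondary cases.
- For pneumococcus, the first symptomatic case may not be the first carrier, and the plan should say so.
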